		5.2.1	Secondary outcome measure of functional independence delayed	Cost of data purchase
1.4	9/29/25	7.5	Primary analysis will not include baseline covariates or random effects for the hospital	Parsimony; model stability
		7.7	Add a complier average causal effect analysis (CACE) to per protocol analysis to test the effect of study protocol compliance	Robustness
		7.10	One-sided alpha changed to a two-sided test	Improve rigor of interpretation
DATA LOCK OCCURS – October 1, 2025				
1.5	10/3/25	5.3	Re-defined dose as game usage during each intervention period instead of based on time spent.	Improve understanding of mediation
		7.1	Remove exploratory analysis of fidelity of intervention receipt; remove mediation analysis of clinical outcomes	Inability to acquire correct statistical package on CMS Virtual Desktop; results preclude necessity

SUMMARY

Study Population: The primary study population consists of 800 board-certified emergency physicians employed at non-trauma centers in the continental US. Outcomes are assessed using Medicare claims from patients aged 65 or older treated by trial physicians during the one-year post-enrollment period.

Design: This is a Phase 3, Type 1 hybrid effectiveness-implementation randomized clinical trial in which physicians are randomized 1:1 to play *Night Shift 2024* (game-based training) or to receive usual education (control). The primary outcome is assessed using Medicare claims data collected for 13 months after the close of enrollment.

Sample Size: A total of 800 physicians (400 per arm) provides 80% power to detect a 7.4% to 10% absolute reduction in under-triage at a one-sided significance level of 0.05, assuming an intraclass correlation coefficient of 0.45 and a median of 1-2 eligible patients per physician.

TABLE OF CONTENTS

1. ABBREVIATIONS	7
2. BACKGROUND AND RATIONALE	8
3. ENROLLMENT CRITERIA	8
3.1. Physician Participants	8
3.1.1. Inclusion criteria	9
3.1.2. Exclusion criteria	9
3.2. Patient Participants	9
3.2.1. Inclusion criteria	9
3.2.2. Exclusion criteria (primary analysis)	9
3.3. Hospital Characteristics	9
3.4. Key Decision Makers	10
3.4.1. Inclusion criteria (must meet at least one of the following)	10
3.4.2. Exclusion criteria	10
4. INTERVENTIONS	10
4.1. Intervention Arm (Game-Based Training)	10
4.1.1. Dosing and administration	10
4.1.2. Measurement of fidelity of treatment delivery	11
4.1.3. Measurement of fidelity of treatment receipt	11
4.2. Control Arm (Usual Education)	11

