7.5. Primary Endpoint Analysis

The primary endpoint (under-triage) is analyzed using a generalized linear mixed model (GLMM) with a binomial error distribution, a logit link function, and an exchangeable correlation structure. The outcome is modeled at the patient level. The fixed effect is treatment arm (game-based training vs. usual education). Random effects are included at the physician and hospital levels to account for clustering of patients within physicians and physicians within hospitals. Random effects are specified as random intercepts only, with an assumption of no covariance between the physician-level and hospital-level random intercepts. This specification was selected as the most parsimonious structure consistent with the nested clustering of patients within physicians and physicians within hospitals, and to minimize the risk of convergence failure given the number of hospital-level clusters in the trial. A random intercepts-only specification is appropriate given that the primary quantity of interest is the fixed treatment effect, and there is no a priori expectation that the treatment effect varies across physicians or hospitals in a way that requires random slopes. If the model does not converge (due to the scarcity of cases within hospitals), we will remove the hospital-level random effect preferentially.

Model estimation is performed in Stata 17.0 using the melogit command adaptive Gauss-Hermite quadrature with the `intpoints(7)` option. Convergence is assessed using the following diagnostics: (1) the final convergence code, which should indicate successful convergence (code = 0 in Stata or equivalent); (2) the number of iterations required to reach convergence; and (3) the scaled gradient at convergence, which should fall below the conventional threshold of 0.001. If convergence is not achieved with the default optimizer and settings, the following pre-specified remediation steps are taken in sequence: (a) increase the number of integration points using the `intpoints()` option; and (b) rescale continuous covariates to have mean 0 and standard deviation 1.

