The primary model will the following baseline covariates: patient-level characteristics (age, sex, age-adjusted Charlson Comorbidity Index score); physician-level characteristics (sex, years of experience, number of shifts per month; and hospital-level characteristics (resource availability, bed size, teaching status). The analysis is conducted on the ITT population. A one-sided hypothesis test is used at a significance level of 0.05.

The test statistic follows a chi-square distribution with degrees of freedom equal to the number of variance parameters removed. Variance components for both random effects, including estimated variances and corresponding intraclass correlation coefficients at the physician and hospital levels will be reported. These results are interpreted as evidence of the degree of clustering of patients within physicians and physicians within hospitals, respectively, and provide empirical justification for the multilevel modeling approach used in this trial.

Protocol Deviation (Version 1.4): We decided to use unadjusted primary model with no baseline covariate adjustment and clustering only at the physician level to ensure transparency and to maximize chances for model stability. In sensitivity analyses we did test the effect of

clustering at the hospital level (patients nested within patients within hospitals), and then assessed variance to determine whether to retain the clustering or not.

Protocol Deviation (Version 1.5): We had pre-specified the use of a one-sided significance test of 0.05. However, during analysis, consistent with the CONSORT guidelines, we used a two-sided test, which corresponds to a one-sided test of 0.025. We disclose this deviation in the Methods of the paper.

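### SAP 7.5 refers the test for removing a random-effect variance to an ordinary chi-square, which doubles the p-value for a single variance tested at zero

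*SAP*

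**What the plan says.** SAP 7.5 sets up a mixed-effects logistic model with physician and hospital levels: "Random effects are specified as random intercepts only, with an assumption of no covariance between the physician-level and hospital-level random intercepts". If that model fails to converge, "we will remove the hospital-level random effect preferentially".

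Later in the same section comes the rule for testing the random effects: "The test statistic follows a chi-square distribution with degrees of freedom equal to the number of variance parameters removed". The section does not name the test, give it a significance level, or mention that a variance of zero lies on a boundary. The 0.05 level in that section belongs to the treatment comparison: "A one-sided hypothesis test is used at a significance level of 0.05".

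The Version 1.4 entry in the revision history then changes the model: "Primary analysis will not include baseline covariates or random effects for the hospital", on grounds of parsimony and stability. The matching deviation note in 7.5 describes "clustering only at the physician level to ensure transparency and to maximize chances for model stability". It adds that hospital clustering was tried in sensitivity analyses, where the analysts "assessed variance to determine whether to retain the clustering or not". No criterion for that decision is stated.

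**The concern.** A variance cannot be negative, so the hypothesis that it equals zero sits at the edge of the parameter space. The usual chi-square result for a likelihood-ratio statistic assumes an interior null value and does not hold here. Using it makes the test conservative: p-values are too large, and the simpler model is favoured.

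The Version 1.4 primary model already omits hospital clustering, and the sensitivity analysis with a hospital intercept is where that choice gets checked. If the retention decision there rests on a test that leans towards no hospital effect, the check is weaker than it appears. SAP 7.6 applies the same model framework to the composite outcome and to over-triage, so the rule would carry over to those analyses if it is used there.

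**Working it through.** The SAP gives no statistic, threshold or p-value for this test, so there is no figure of its own to reproduce. The check compares the stated reference distribution with the correct one.

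**Inputs**
- Stated reference: chi-square, one degree of freedom per variance removed (SAP 7.5).
- Structure: independent random intercepts, so dropping the hospital level removes one variance and no covariance (SAP 7.5).
- Test: read as a likelihood-ratio comparison of nested models. This is an inference from the reference to parameters removed.
- Level: 5%, assumed.

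**One variance removed (hospital)**

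Under the null, the variance estimate falls on zero about half the time and the statistic T is then 0. Otherwise T behaves as chi-square with 1 df. For any c > 0:

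P(T > c) = 0.5 × P(χ²₁ > c)

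- 5% critical value: 0.5 × P(χ²₁ > c) = 0.05 gives c = 2.706. The SAP's rule uses 3.841.
- True size at 3.841: 0.5 × 0.05 = 0.025.
- The correct p is half the SAP's p at every positive statistic: 0.10 becomes 0.050, 0.07 becomes 0.035, and 0.05 becomes 0.025.
- At 5%, the two rules disagree only when 2.706 < T < 3.841, that is, when the SAP's p lies between 0.05 and 0.10.

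**Both variances removed (independent approximation)**

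P(T > c) = 0.5 × P(χ²₁ > c) + 0.25 × P(χ²₂ > c)

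- 5% critical value: c = 4.231, against the SAP's 5.991.
- True size at 5.991: 0.0072 + 0.25 × 0.05 = 0.0197, so a stated p of 0.05 is too large by a factor of 0.05 / 0.0197 = 2.54.

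**Does the asymptotic result hold in sparse data?**

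A simulation fitted three-level logistic models with and without a hospital intercept. The assumed design was 200 hospitals, 3 physicians each and 1 to 3 patients per physician. None of these counts is in the documents, apart from the SAP 7.2 median of 1-2 patients per physician. The physician SD comes from the SAP 7.2 intraclass correlation of 0.45, read on the latent scale: variance = (π²/3) × 0.45 / 0.55 = 2.69, so SD = 1.64.

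| True hospital SD | Runs | T > 3.841 (SAP rule) | T > 2.706 (mixture) |
|---|---|---|---|
| 0 | 5,060 | 2.2% | 4.3% |
| 0.5 | 2,906 | 12.8% | 19.8% |

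With no hospital effect, about 53% of the statistics were zero, close to the 50% that theory predicts. The two rules reached different decisions in 4.3 − 2.2 = 2.1% of runs with no hospital effect, and in 19.8 − 12.8 = 7.0% of runs with SD 0.5. With SD 0.5, the SAP's rule missed the hospital effect in 87.2% of runs and the corrected rule still missed it in 80.2%.

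**The case against.** The strongest objection concerns consequences, not theory.

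- **The link to the retention decision is not stated.** The Version 1.4 note says only that variance was assessed. It names no likelihood-ratio test, p-value or threshold, and the analysts could have looked at the estimate or the intraclass correlation. The chi-square sentence belongs to the two-level specification, while the retention wording is in a later deviation note. This stands, so the effect on retention is conditional.
- **The primary model did not lose its hospital effect through this test.** A reader might infer that the faulty reference led to the physician-only primary model. The documents do not support that. The hospital effect was removed by decision, for parsimony and stability, and non-convergence is a separate ground for removing it.
- **No published p-value is shown to be wrong.** A reader might infer that the results offered as support for multilevel modelling are invalid. In SAP 7.5 those results are most naturally the variances and intraclass correlations named in the sentence just before. Neither depends on the reference distribution, and the section promises no p-value for this test.
- **Low power matters more than the reference.** In the assumed scenario even the corrected test misses most hospital effects, so halving the p-value alone would not make a test-based rule safe. This also stands, and it shapes the fix.

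None of this makes the stated reference correct. The sentence gives a distributional rule, and for a variance tested at zero the rule is wrong.

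**Conclusion.** Wrong as written, with limited reach. For removal of the hospital variance, the stated reference doubles the p-value, and a nominal 5% test has true size 2.5%. If both variances are removed together, the size is about 2.0% under the independent approximation.

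The effect is confined to the hospital-level sensitivity analysis, and arises there only if this test informed the decision to keep or drop hospital clustering. In that case the rule leans towards dropping it, and at 5% the decision would differ only for a statistic between 2.71 and 3.84. The documents do not show whether that happened. The primary treatment p-value and the reported variances and intraclass correlations are unaffected.

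The conclusion assumes that the unnamed test is a likelihood-ratio test. The size figures also assume a 5% level, and the simulated detection rates rest on assumed numbers of hospitals and physicians.

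**What to change.** In SAP 7.5:

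1. Name the likelihood-ratio test and state its significance level.
2. Replace the reference distribution. For one variance, use the 50:50 mixture of chi-square with 0 and 1 df, which means halving the 1-df p-value. If both variances are removed, use the mixture appropriate to that case.
3. Report the hospital-clustered sensitivity model whenever it converges, alongside the physician-only primary model, so that a low-power test does not decide whether readers see it.
4. State how variance was assessed in the Version 1.4 step, so that a reader can tell whether this test played any part.

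The cost is one or two sentences and one extra reported model. Any one-variance p-value already computed can be corrected by hand. Step 3 makes the retention decision independent of the test, but step 2 is still needed for any p-value that is reported.

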7.6. Secondary Endpoint Analysis

7.6.1. Patient outcomes

The composite 30-day mortality and readmission outcome and functional dependence are each analyzed using the same GLMM framework as the primary endpoint, with the respective binary outcome as the dependent variable.

7.6.2. Safety outcomes

Over-triage is analyzed using the same GLMM framework, with the proportion of minimally injured patients transferred to a trauma center as the dependent variable.

Protocol Deviation (Version 1.3): We did not test functional dependence as a secondary clinical outcome.

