Secondary (outcome analysis) - The proportion of patients over-triaged by physicians in the game-based training group will be equivalent to the proportion over-triaged by physicians in the usual care group

Secondary (mediation) - Under-triage will mediate the effect of the intervention on patient-centered outcomes.

Exploratory (heterogeneity of treatment effect) -

- [1] The intervention will have the same effect on males as on female trial participants.
- [2] The intervention will have the same effect on White compared as on non-White trial participants.
- [3] The intervention will have a greater effect on trial participants who expressed positive attitudes to game-based learning before enrollment compared to those who do not have positive attitudes.
- [4] Trial participants in the game-based training group who use Night Shift 2024 for greater than 2 hours will under-triage a smaller proportion of severely injured patients than those who use the game for less than 2 hours.
- [5] The proportion of patients under-triaged by trial participants will be lower immediately after exposure to the intervention (i.e., in the first 30 days) compared to late post-exposure period (i.e., 30-89 days).
- [6] Trial participants with greater parameters of compliance on SONAR (the experimental tool to measure determinants of physicians' decision making) will under-triage a smaller proportion of severely injured patients than those with lower parameters of compliance.

**2. \* Describe the relevant prior experience and gaps in current knowledge including preliminary data. Provide for the scientific or scholarly background for, rationale for, and significance of the research based on existing literature and how it will add to existing knowledge:**

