**3. Describe the primary and secondary study endpoints:**

Primary end-point: under-triage of severely injured patients treated by trial participants.

Second end-points: over-triage of severely injured patients treated by trial participants; 30-day mortality and 30-day readmission of severely injured patients (composite end-point) treated by trial participants; functional independence of severely injured patients, treated by trial participants, at discharge among those with independence prior to the injury.

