**5. List the inclusion criteria:**

Intervention/Control: We plan to recruit board-certified physicians who work exclusively in the EDs of non-trauma centers in the US, and who triage adult trauma patients as part of their practice.

Interviews:

-ED directors at non-trauma centers, trauma directors at Level I/II trauma centers, first responders (paramedics)

-Patients (65 and older) and/or surrogates who were recently treated at a non-trauma center for a traumatic injury using Pitt+Me

Medicare beneficiaries (65 and older) who were treated by study physicians, with an Inpatient or Outpatient claim filed between 2023-2024 in which one of the discharge diagnoses is associated with a moderate to severe injury. We will provide ResDac with a validated crosswalk between ICD10-CM diagnoses codes and the severity of injury to identify the relevant patients.

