5.2.2. Safety outcome

- **Over-triage:** The proportion of patients with minimal injuries who are transferred to a trauma center, assessed to evaluate potential harm associated with the intervention.

Protocol Deviation (Protocol Deviation 1.3): The ClinicalTrials.gov registration (NCT06063434) and original statistical analysis plan included functional independence as a secondary clinical outcome that that we did not measure, because we could not purchase Medicare Skilled Nursing Facility claims.

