7. STATISTICAL ANALYSIS PLAN

7.1. Statistical Objectives

The primary statistical objective is to determine whether physicians randomized to *Night Shift 2024* under-triage a smaller proportion of severely injured older patients compared to those receiving usual education, as assessed using Medicare claims data over the one-year post-

enrollment period. Secondary objectives are to evaluate the effect of the intervention on patient outcomes (30-day mortality and readmissions, functional dependence) and to assess safety (over-triage).

Exploratory objectives include evaluating: 1) the heterogeneity of treatment effect across pre-specified physician-level subgroups; 2) the mediation of the intervention's effect by dose, time between game usage and treatment of patient, and fidelity of intervention receipt; 3) the mediation of clinical outcomes by the intervention

Protocol Deviation (Version 1.3 and 1.5): We did not assess the effect of the game on functional dependence, mediation by fidelity of intervention receipt, or mediation by the game.

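### Over-triage is hypothesised to be equivalent between arms, but the SAP analyses it as a difference with no margin or confidence-interval rule, so a non-significant result cannot support the hypothesis

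*SAP*

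**What the plan says.** **Hypothesis.** The Protocol (Study Aims, item 1) lists as a secondary hypothesis that the proportion over-triaged by physicians in the game group "will be equivalent to the proportion over-triaged by physicians in the usual care group".

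**Role.** SAP 5.2.2 makes over-triage the only safety outcome, "assessed to evaluate potential harm associated with the intervention". The objectives in SAP 7.1 name it as the safety assessment and do not carry over the equivalence wording.

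**Analysis.** SAP 7.6.2: "Over-triage is analyzed using the same GLMM framework, with the proportion of minimally injured patients transferred to a trauma center as the dependent variable". The framework it borrows is in SAP 7.5, where the original rule was "A one-sided hypothesis test is used at a significance level of 0.05". A deviation note in the same section reports that "we used a two-sided test, which corresponds to a one-sided test of 0.025". Nothing is said about which of these applies to over-triage, or in which direction.

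**Population.** Protocol Study Design item 3 describes the endpoint as "over-triage of severely injured patients treated by trial participants", whereas SAP 5.2.2 and 7.6.2 use minimally injured patients. Protocol Study Design item 5 restricts the claims to those in which "one of the discharge diagnoses is associated with a moderate to severe injury". The Patients part of the Protocol's Research Activities, its Medical Records item 1 and SAP 3.2.1 all take claims for injury codes without a severity limit.

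**The concern.** A test of no difference and a demonstration of equivalence answer different questions. Failing to reject the first says only that the data are compatible with no difference; they may be equally compatible with a harmful increase. Without a margin, the less precise the data, the easier it is to obtain a result that looks like the hypothesised one.

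This matters because over-triage is the trial's check on harm. SAP 7.7.3 names two routes by which the game could lower under-triage: better discrimination of severe injury, or a greater willingness to transfer. The second could also raise unnecessary transfers. The mediation analysis meant to separate the two was deferred (SAP 7.7.3, Version 1.5 deviation). The over-triage comparison is then the main claims-based evidence on the point, and it has no rule for reaching a conclusion.

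**Working it through.** **1. Does anything in the plan supply a decision rule?** The places where one could stand:

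- Protocol, Study Aims: equivalence stated, no margin.
- Protocol, Study Design item 8, and SAP 7.2: sample size for under-triage only.
- SAP 7.5 and 7.10: sidedness and alpha for the primary test only.
- SAP 7.6.2: model named; no margin, direction or CI rule.
- SAP 7.7: 95% CIs promised, but for the exploratory analyses.

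So no rule exists. If the original one-sided test were carried over in the direction of benefit, it could not flag an increase in over-triage at all.

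**2. The plan's own figure, for under-triage.** Inputs from SAP 7.2: 400 physicians per arm, at least 75% contributing (300), 1–2 patients each, ICC 0.45, one-sided 0.05. Effective n per arm = physicians × m / (1 + (m − 1) × ICC). The sample-size text gives no baseline rate; I take 50% from SAP section 2.

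- 400 × 2 / 1.45 = 552: power for 7.4 points is 79.5%.
- 300 × 1 = 300: power for 10 points is 79.4%.

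The stated 7.4–10 points at 80% power is reproduced under that baseline. It concerns severely injured patients and says nothing about precision for over-triage.

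**3. Over-triage, illustration only.** Every over-triage input is an assumption: rate p of 5% or 10%, 300 contributing physicians per arm, 2–20 minimally injured patients each, ICC 0.05–0.45. Effective n per arm:

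- 300 × 2 / (1 + 1 × 0.45) = 414
- 300 × 5 / (1 + 4 × 0.05) = 1,250
- 300 × 20 / (1 + 19 × 0.05) = 3,077

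With SE = √(2p(1 − p)/n), the 95% half-width is 1.96 × SE. The smallest margin demonstrable with 80% power by two one-sided 5% tests, true difference zero, is (1.645 + 1.282) × SE. The last column is the chance that a two-sided 5% difference test is non-significant although over-triage truly rises by 2 points.

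| Rate | Effective n per arm | 95% half-width (points) | Smallest margin (points) | Chance of missing +2 points |
|---|---|---|---|---|
| 5% | 414 | 2.97 | 4.43 | 77% |
| 5% | 1,250 | 1.71 | 2.55 | 44% |
| 5% | 3,077 | 1.09 | 1.63 | 9% |
| 10% | 414 | 4.09 | 6.10 | 85% |
| 10% | 1,250 | 2.35 | 3.51 | 64% |
| 10% | 3,077 | 1.50 | 2.24 | 29% |

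If the under-triage ICC of 0.45 also applied here, effective n could not exceed 300/0.45 = 667 per arm (400/0.45 = 889 if every physician contributed), however many minor injuries each saw. At a 5% rate the half-width at 667 is 1.96 × √(2 × 0.05 × 0.95/667) = 2.3 points. The documents do not say that this ICC applies to over-triage.

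**4. Population.** Set side by side, the Protocol's endpoint names severely injured patients and the SAP's names minimally injured ones. The Protocol's inclusion criterion would leave out minor injuries, while its own data description and SAP 3.2.1 would bring them in. Neither document gives an ISS cut-off for minimal injury.

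**The case against.** The best defence is that SAP 7.6.2 names a model, not a superiority test. A GLMM yields an estimate and a confidence interval, from which equivalence or non-inferiority can be judged. The SAP itself speaks only of assessing safety, so on its own terms it makes no equivalence claim. The outcome is secondary and the primary analysis is untouched.

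The point about the model stands: nothing is wrong with the GLMM. It does not remove the gap, because the Protocol's equivalence hypothesis is still on record and no document says what interval would satisfy it.

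Four stronger readings are tempting, and the documents do not support them:

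- *The trial is underpowered for over-triage.* Not shown. The 1–2 patients per physician are severely injured; the number with minor injuries is unstated. If they are many and weakly clustered, the interval may be narrow.
- *A null will be reported as no harm.* Neither document says so. The SAP does describe null clinical outcomes in that way (7.7.4 and the Appendix), which makes the risk plausible, but those remarks do not concern over-triage.
- *The game pushes physicians towards transfer.* SAP 7.7.3 says that it targets diagnostic ability. A shifted threshold is a possible side effect, not the stated mechanism.
- *The claims data lack minimally injured patients.* Only Protocol Study Design item 5 points that way; the Protocol's Research Activities and Medical Records sections and SAP 3.2.1 point the other way. This is a conflict to reconcile, not evidence of a missing denominator.

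**Conclusion.** The concern holds in a limited form. The Protocol states an equivalence hypothesis for the only safety outcome, and the plan contains no procedure that could support it. That conclusion rests on the text alone and needs no assumption about rates or sample size.

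How much it matters numerically is open. Over the assumed range, a 2-point increase could be missed anywhere from 9% to 85% of the time. That shows why a p-value cannot stand in for a margin; it is not an estimate for this trial.

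Timing limits the remedy. The SAP's transparency note says that it was reconstructed after trial completion, SAP 7.7.4 shows that clinical results were known, and the Appendix lists over-triage among the manuscript's outcomes. Any margin set now is post hoc.

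**What to change.** 1. In SAP 7.6.2, and in the manuscript, report the over-triage risk difference between arms with its two-sided CI, obtained from the fitted model by averaging predicted probabilities. State the CI level.
2. State that neither equivalence nor absence of harm will be concluded from a non-significant p-value.
3. Claim equivalence, or no worse, only if the CI (its upper limit, for harm) lies inside a margin set by people who have not seen the over-triage results, and label that margin post hoc. If this cannot be done, withdraw the equivalence hypothesis and give the estimate and CI alone.
4. Reconcile Protocol Study Design item 3 with SAP 5.2.2 and 7.6.2 on whose over-triage is measured, and give the definition of minimal injury that was used. Reconcile Protocol Study Design item 5 with the Protocol's Research Activities and Medical Records sections and SAP 3.2.1 on which injury claims are included.

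The cost is wording plus one interval from a model already fitted; no new data are needed. The downside is that the trial may be unable to claim equivalence.
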